6.5 Randomisation

Participants will be randomised as close to the planned operation as possible (ideally 30 minutes before the participant is taken to theatre), after consent has been given, baseline assessments have been completed and eligibility has been confirmed by the Principal Investigator, a delegated medically qualified doctor or Advanced Nurse Practitioner who has undergone suitable training.

Participants will be allocated in a 1:1 ratio to either CDI plus standard de-airing or medical air insufflation (placebo) plus standard de-airing. The allocation will be computer-generated and will be stratified by centre, type of procedure (i.e. valve only or valve combined with another procedure e.g. CABG) and whether planned surgical access is minimally invasive (e.g. thoracotomy), by an independent BTC CTEU statistician, not involved in the study, before recruitment begins.

Randomisation will be performed using a secure internet-based randomisation system ensuring allocation concealment by a member of the research team not involved in data collection or participant follow-up.

6.6 Blinding

Participants, their clinical care team (i.e. the surgeon, anaesthetist and those responsible for their post-operative care), research nurse(s) responsible for participant follow-up and imaging assessors will not be informed of the intervention allocation.

The perfusionist will be unblinded to the trial intervention allocated at randomisation in order to deliver the allocated intervention and monitor the participant throughout the surgery. Either the perfusionist or an unblinded member of the team will be responsible for carrying out the randomisation and preparing the unblinded case report form (CRF) with the treatment allocation. If an unblinded member of the team randomises the participant, they will hand documentation containing the treatment allocation and the relevant CRF in a sealed envelope to the perfusionist.

Following surgery the completed CRF will be entered into the database by either the perfusionist or the unblinded member of the team. This documentation will be stored separately to the rest of the CRFs to ensure blinding is maintained throughout the trial.

Any member of staff who accesses the sealed envelope containing the allocation details will have to record the reason for accessing the documentation on the relevant case report form.

Cylinders of carbon dioxide and medical air can be purchased in similar physical sizes, both are grey in colour and only the collars differ. The cylinder will be brought into theatre by the Perfusionist. The cylinder and flowmeter will be covered with a sterile surgical drape/sleeve to maintain blinding. The insufflation flow rate will be standardised for both groups (5L/min).

There are no obvious clinical or other cues as to whether CDI or medical air was used, so we do not expect participants to be unblinded. Research Nurses responsible for data collection and participant follow-up will not randomise patients and will not be in the operating theatre. MRI scans will be analysed centrally. We will assess the success of blinding by asking the Research Nurse undertaking the assessments, after the three month follow up, and the Imaging Assessor, following review of the DW-MRI brain, which treatment they think was received (Bang blinding index (27)).

6.7 Unblinding

Requests to unblind on clinical grounds, e.g. to treat a complication, are not anticipated. However, if unblinding is requested during surgery on safety grounds, this will be facilitated by the Perfusionist. Any such request will be fully documented including who requested the unblinding and the reason for unblinding.

Requests to unblind after leaving the operating theatre should not occur; given that the effect of CDI/medical air insufflation is strictly limited to the period of delivery in the operating room. Therefore, the management of any subsequent SAE would not be altered by knowledge of the allocation. Unblinding rates will be monitored throughout the trial by the study team and by the independent Data Monitoring and Safety Committee (DMSC) that will be established to oversee participant safety in the trial (see Section 11 for further details).

Participants will be made aware before entering the study that they will not be told which treatment they will receive until after the trial has completed.

6.8 Research procedures

Participants will be required to do, or undergo, the following tasks or investigations specifically for the study which are also outlined in table 1.

Pre-surgery:

- Read the CO2 study PIL (can be sent to the patient's home before the patient attends the hospital for their surgery)
- Provide informed consent to participate, if willing to do so
- Assessment of NIHSS, CAM, functional status (Barthel Index) and neurocognitive function (ACE III and TMT A&B)
 Complete quality of life questionnaire (SF-12)

During surgery:

- Receive the intervention allocated at randomisation during open heart valve surgery
- If participating in the mechanistic sub-study (Bristol centre only), a transcranial doppler ultrasound of the middle cerebral artery and near infrared spectroscopy of the frontal lobe will be conducted during surgery
- Assessment and reporting of any AEs and SAEs experienced

Post-surgery inpatient stay:

- Day 3 (between 3-5 days post-surgery): Assessment of NIHSS and CAM
- DW MRI brain scan ideally between 2 and 7, but no more than 10, days after surgery before hospital discharge
- Assessment and reporting of any AEs and SAEs experienced

Post-discharge:

Three months post-surgery (conducted remotely): Assessment of NIHSS, CAM, functional status (Barthel Index) and neurocognitive function (ACE III and TMT A&B) Complete quality of life questionnaire (SF-12).

Collection and assessment of any SAEs experienced after discharge from hospital

6.8.1 Neurocognitive function

Neurocognitive function tests, assessing six domains; visual and verbal memory, executive functioning, visuospatial or constructional praxis, attention and information processing speed, will be performed by a member of the research team who has undergone suitable training.

The tests to assess neurocognitive function are:

- Addenbrooke's Cognitive Examination III (28)
- Oral trail making test part A and B (29, 30)

Tests will be performed prior to surgery and at three-month follow up and should take around 30 minutes to conduct.

6.8.2 National Institutes of Health Stroke Scale

National Institutes of Health Stroke Scale (NIHSS) will be used to assess any impairment that may have been caused by ischemic brain injury. The scale will be completed at the specified timepoints by a member of research team who has undergone suitable training. The scale should take around 15 minutes to conduct.

6.8.3 Confusion Assessment Method

Delirium will be assessed using the confusion assessment method algorithm three minute interview (31). The interview will be performed at the specified timepoints by a member of research team who has undergone suitable training. The interview should take around three minutes to conduct.

6.8.4 Functional status

Functional status will be assessed using the Barthel Index (32). The index will be performed at the specified timepoints by a member of the research team who has undergone suitable training. The score should take around 10 minutes to conduct.

6.8.5 Patient reported outcomes

Quality of life (QoL) will be assessed using the physical and mental subscales of the 12-item Short-Form Health Survey (SF-12) (33). The patient should complete the questionnaire prior to surgery and at three-month follow up. Participants will be able to choose to receive the QoL questionnaire at three months by post (sent by BTC CTEU) or complete online via a secure website.

6.8.6 Diffusion Weighted Magnetic Resonance Imaging (DW MRI)

All participants will undergo a 1.5 or 3.0 T diffusion weighted MRI (DW MRI) scan of their brain post-surgery. The DW MRI scan should be conducted in accordance with the CO2 MRI protocol. The scan will take approximately 30 minutes and will be completed as an inpatient as soon as possible after their surgery, ideally between 2-7 but no more than 10 days following surgery.

Scans will be transferred to the Wellcome Centre for Integrative Neuroimaging at the University of Oxford, who will perform a blinded review to assess any radiographic evidence of brain injury following surgery. Instructions on the transfer of images will be outlined in the imaging manual.

Participants will be asked to consent to the transfer of their DW MRI brain scans for review at entry to the trial.

6.8.7 Mechanistic sub-study – Bristol centre only

One-hundred study participants from the Bristol centre will be asked to take part in the CO2 mechanistic sub-study. Consent to the sub-study is optional.

Sub-study participants will undergo a transcranial doppler (TCD) ultrasound of the middle cerebral artery during their surgery to monitor intraoperative air microemboli load and CBF. Participants will also undergo near-infrared spectroscopy (NIRS) to monitor the TOI of the frontal lobes during surgery.

The TCD and NIRS probes will be placed on the participant's head and secured before insufflation is initiated, until the procedure has been completed. Sub-study assessments will be performed by a Surgeon and Research Fellow who have undergone suitable training.

6.8.8 Non completion of research procedures

Reasons for not completing any research procedure will be recorded and coded where possible. Missing items or errors on questionnaires will be dealt with according to the scoring manual or via imputation methods. Adherence rates will be reported in the results, including the numbers of patient who have withdrawn from the study, been lost to follow up or died. Causes of death will be recorded.

6.8.9 Abnormal findings

Any abnormal findings identified because of the study assessments will be escalated to the relevant care teams for further investigation.

7. Trial intervention

7.1 Trial interventions

Study participants will be randomly allocated on a 1:1 ratio to receive insufflation with either:

- **IMP:** Medical carbon dioxide (carbon dioxide purity 99.5% v/v min)
- Placebo: Medical air (oxygen content 21%)

7.1.1 Dosing schedule

Insufflation, with either carbon dioxide or medical air, will be initiated at a flow rate of 5 litres per minute (5.0L/min) before cannulation for cardiopulmonary bypass (CPB) and continued until 10 minutes post-CPB.

The allocated gas will be insufflated into the cardiothoracic wound through a gas diffuser that provides an almost 100% carbon dioxide / medical air atmosphere in the wound, as per the centre's local procedure.

The diffuser will be placed in the inferior part of the surgical incision.

When applied, the cardiotomy suction will be limited to a maximum rate of 1.5 L/min and the rough suction will be set to 10 L/min to avoid affecting the carbon dioxide/air concentrations in the field.

7.1.2 Surgical procedure

Operations will be performed through a complete or limited median sternotomy or thoracotomy with CPB with either a roller or centrifugal pump and hollowfibre membrane oxygenator maintaining non-pulsatile perfusion at 2 to 3L/(min m2), an arterial line filter will be used, mean arterial pressure maintenance at 70 and 90 mm Hg, and patient temperature to be between 37°-32°C. Gas sweep flows will be adjusted to maintain PaCO2 at 35-40 mmHg (4.6-5.2KPa) with the alpha stat method.

Standard cannulation will consist of arterial cannulation in the distal part of the ascending aorta and a 2-stage venous cannula inserted into the right atrium and the inferior venae cava. Mitral valve operations will be an exception, for this surgery bicaval cannulation will be used.

Peripheral cannulation will be carried out as per local procedure in minimally invasive procedures i.e. using the femoral artery.

Myocardial preservation will be achieved with intermittent antegrade and retrograde cold blood cardioplegia.

7.1.3 De-airing manoeuvres

Surgeons should perform standard de-airing manoeuvres such as the following.

The CO2 study Protocol Version 6.0 23 Nov 2021

Following completion of the surgical procedure, the heart is passively de-aired across the aortic or left atrial suture line as follows:

- With the LV and root vents clamped, and any caval tapes unsnugged, the heart is filled with blood by occlusion of the venous return and the lungs are ventilated.
- The LV and LAA are then massaged, and the left heart de-aired across the aortic/left atrial suture line before the suture is tied.

After the suture line has been tied, and in Trendelenburg position, the heart is again filled and the lungs ventilated whilst maintaining suction on the root vent. Complimentary deairing of the apex is achieved by brief and low suction on the LV vent, which is stopped before removal of the aortic clamp. After removal of the cross clamp, the aortic suction is maintained at 200-300ml/min. The LV vent can be opened for brief periods if the LV distends, but prolonged suction should be avoided when the heart is empty to prevent air from entering the LA around the vent. Gravity drainage of the LV vent (rather than suction) will prevent air being entrained and is acceptable when the heart is empty.

Additional deairing during the rewarming period is by maintaining aortic root vent suction.

When the trans-oesophageal echo (TOE) shows that all microbubbles have been evacuated, the LV vent can be removed.

The aortic root vent is maintained until the patient is totally weaned from cardiopulmonary bypass.

All other aspects of the participant's pre, intra and post-operative management will be in accordance with existing local protocols.

7.1.4 Dose modifications

Dose modifications are not expected to occur.

7.1.5 Regulatory status

Medical carbon dioxide and medical air are UK-licensed and commercially available on the UK market. For this trial it is acceptable to use any licenced supply of medical carbon dioxide or medical air

In this trial, medical carbon dioxide and medical air will be used 'off label' as part of the openheart valve repair or replacement surgery.

7.1.6 Preparation and labelling

It is recommended that cylinders of both trial interventions are ordered in the same size to prevent unblinding. If using BOC ltd supplied gas, cylinder size E is recommended.

The CO2 study Protocol Version 6.0 Two cylinders of the allocated trial intervention should be taken into the operating theatre to ensure sufficient supply is available for the procedure. Green tubing can be used to connect to both cylinders with a Y connector ensure flow can be continuously delivered without unblinding, should both cylinders be required.

Surgical drapes should be placed over the cylinders before they are brought into the operating theatre to prevent unblinding.

All cylinders will be labelled, in the cylinder storage area, under the supervision of the site's trial pharmacist with annex 13 compliant labels and in accordance with Good Clinical Practice (GCP) and pharmacy department SOPs.

The contents of the label will be submitted and approved for use by the MHRA.

7.1.7 Drug storage and supply

Both carbon dioxide and medical air will be sourced locally by the research site pharmacy (or as per local pharmacy delegated arrangements) at market price. Supply levels should be monitored and re-ordered as applicable.

Carbon dioxide and medical air cylinders will be stored and handled as per the current SPC storage precautions, in accordance with GCP, Good Manufacturing Practice and pharmacy department SOPs.

7.1.8 Reference Safety Information

Reference safety information, listed in the medical carbon dioxide SPC, section 4.8 undesirable events, are not applicable to the trial population given that these patients will be unconscious due to anaesthesia and on CPB at the time the trial intervention is received and therefore, cannot experience the listed side effects.

No expected events are listed in the medical air SPC section 4.8, 'undesirable events'. Section 4.8 of the medical carbon dioxide and medical air SPC will be regularly reviewed for updates to the undesirable events listed. If there are any updates these will be reviewed by the Chief Investigator and, in consultation with the Sponsor, a decision made whether the updated document will be submitted to the MHRA for use as the RSI in the trial.

7.1.9 Contraindications

Participants who are known to have acquired or genetic acidosis (i.e. renal tubular acidosis) will be excluded from the trial.

7.1.10 Treatment adherence

Withdrawals during treatment should not occur due to the nature and duration of the intervention; the duration of intervention is from before cannulation for CPB, until 10 minutes

The CO2 study Protocol Version 6.0 after CPB has stopped. Problems with adherence (e.g. failure to follow randomisation allocation) are also expected to be low. The Perfusionist will document whether the allocated treatment was given, if there were any deviations from the allocated intervention and the reason.

7.2 Duration of treatment period

The duration of the treatment commences when the patient enters the operating room and concludes when the patient leaves the operating room after their surgery.

The duration of the procedure is expected to be between 2 hours and 4 hours.

Table 1 Schedule of assessments

			Post-surgery				
	Baseline	Intraoperative	Day 3 (between 3-5 days post op)	Day 2 – 7 (but no more than 10 days)	Discharge	Routine post-op follow-up	Three- month follow up
National Institutes of Health Stroke Scale	✓		✓				✓
Confusion Assessment Method	✓		✓				✓
Functional status: Barthel Index score	✓						✓
Neurocognitive function tests: Addenbrookes Cognitive Examination III and oral Trail Making Tests A&B	✓						√
Quality of life questionnaire (SF-12)	✓						✓
Assessment of post-operative complications					✓		
DW MRI brain				✓			
Assessment of serious adverse events (from randomisation to three month follow up), including readmissions			√	√	√	√	✓
Assessment of blinding success							✓
Transcranial doppler ultrasound*		√					
Near-infrared spectroscopy*		✓					

^{*100} patients at the Bristol centre only

8. Data collection

Each patient will be assigned a unique study number. All data recorded on paper relating to the participant will be located in CRF folders, which will be stored securely. Staff with authorisation to make changes to the study records, including the study database, will be listed on the study delegation log maintained at each centre.

Screening data will be collected for all patients undergoing open heart valve surgery considered for the study. Age, sex and Index of Multiple Deprivation (IMD) will be collected for all patients irrespective if they decline to participate. This information is collected to assess any difference in the patients that do not take part compared to patients that do, to establish if there are any socioeconomic barriers to participation.

Baseline data will be collected after consent. Consenting patients will be contacted by an authorised member of the local research team (as specified in the delegation log) who will provide the opportunity to understand the nature, significance, implications and risks of the trial so that they may make an informed decision if they should take part. If the patient decides to take part the member of the local research team will obtain informed consent.

Patients who choose to consent using electronic consent methods will verbally provide their email address to the local research team to receive a link to the electronic consent form.

Data collection will include the following elements:

- a) A screening log of all patients undergoing open heart valve surgery via partial or full sternotomy including age, sex and Index of Multiple Deprivation (IMD) for place of residence derived from the patient's residential postcode, as recorded in their hospital records.
- b) Patients approached and assessed against the eligibility criteria and, if ineligible, reasons for ineligibility.
- c) Consent information collected prior to randomisation for all participating patients.
- d) Baseline information (e.g. medical history and assessments) and neurocognitive function and quality of life (collected via questionnaire) collected for all participating patients.
- e) Data relating to surgery and hospital stay collected for all participating patients.
- f) Images from the post-operative DW MRI brain scan will be collected for all patients.
- g) Data on neurocognitive function and quality of life (collected via questionnaire), adverse events and resource use will be collected at three months post-surgery for all participating patients. Participants will be able to choose to receive the quality of life questionnaire by post or complete via an online secure website.

8.1 Definition of end of trial

The definition of the end of the trial is the date when all patients have completed the three-month post-surgery follow-up, or are lost to follow-up, the database has been locked and all data gueries have been resolved.

The end of the trial for an individual patient is defined as completion of the three-month postsurgery follow-up assessments. Patients will be asked to consent to the collection of long term follow up data (via Government bodies NHS Digital, ISD Scotland or NHS Wales Informatics Service) for up to five years post-surgery for future ethically approved research.

9. Safety reporting

9.1 Overview

Serious and adverse events (AEs) will be recorded and reported in accordance with GCP guidelines and the BTC CTEU's Serious Adverse Events and Safety Reporting Standard Operating Procedure (SOP-GE-012) (see Figure 2).

9.2 Definitions

Adverse event (AE) is any undesirable event in a subject receiving treatment according to the protocol, including occurrences which are not necessarily caused by or related to administration of the research procedures.

Adverse reaction (AR) is any undesirable experience that has happened to a subject while taking a drug that is suspected to be caused by the drug or drugs.

Serious adverse event (SAE) is any event which results in death, is life threatening, requires hospitalisation or prolongs hospitalisation, results in persistent or significant disability or incapacity.

Suspected serious adverse reaction (SSAR) is any serious adverse event that is suspected to be related to the drug or drugs being taken.

Suspected unexpected serious adverse reaction (SUSAR) is an untoward medical occurrence suspected to be related to the drug or drugs being taken that is not consistent with the applicable product information and is serious.

All AEs must be reviewed, and causality must be assessed by the Principal Investigator or delegated individual.

If an event meets any of the 'serious' criteria listed below it is classified as an SAE:

- a) Results in death
- b) Life threatening
- c) Requires hospitalisation (unless hospitalisation is pre-planned)
- d) Prolongation of existing hospitalisation
- e) Results in persistent or significant disability or incapacity
- f) Congenital anomaly / birth defect
- g) Any other event which may jeopardise the patient or require intervention to prevent one of the other outcomes listed above

[figure not shown]

Figure 2. Serious adverse event reporting flow chart

Note: ALL adverse events that result in DEATH must be reported on SAE forms to the Sponsor

9.3 Period for recording adverse events

Data on adverse events will only be collected for the period of the participant's post-operative hospital stay.

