2.4 Review of existing evidence

We have conducted and recently published a systematic review and meta-analysis of all available RCTs investigating the efficacy of CDI versus standard de-airing techniques (21). Outcomes investigated were post-operative stroke, neurocognitive dysfunction, and in-hospital mortality. Pooled estimates were obtained using random-effects models to account for clinical diversity and methodological variation between studies. Eight RCTs were identified comparing CDI vs. standard de-airing but only four studies reported on the incidence of post-operative neurocognitive decline (23-25); 283 randomised to CDI, 284 randomised to standard de-airing. Most studies were small (<100 patients) and at high risk of bias. Type and timing of neurocognitive function tests varied among studies. Different methods were used for delivery of carbon dioxide. In-hospital mortality was 2.1% vs 3.0% in the CDI and standard de-airing (control) groups, respectively (risk difference (RD) 0%; 95% CI -2% to 2%. Incidence of stroke was 1.0% vs 1.2% (RD 0%; 95% CI -1% to 2%) and neurocognitive dysfunction was 12% vs 21% (RD: -7%; 95% CI -0.22% to 8%) in the CDI and control group, respectively. The results of the meta-analysis were influenced by our decision to include a trial with no events (23), which resulted in a more conservative estimate of treatment effect. Excluding this trial from the analysis suggested a protective effect of CDI on neurocognitive function (OR 0.46, 95%CI 0.22 to 0.96).

3. Rationale

Nearly 40,000 people in the UK (http://bluebook.scts.org/) and many more worldwide have cardiac surgery annually. Ischaemic brain injury represents a common complication and is associated with increased hospital stay, slow recovery, poor quality of life, further health care resource use and reduced long term survival. Cardiac surgery is increasingly being offered to older, higher-risk patients with comorbidities, so the incidence of neurological complications is likely to increase in the future. CDI is a widely used intervention, which many surgeons believe improves neurological outcomes. However, there is little evidence for its efficacy or risk of harm and its routine use is not recommended and surgeons are currently in equipoise regarding its adoption.

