5.1.2 Secondary outcomes

Data will be collected to characterise the following secondary outcomes:

- 1. Number and volume of DWI brain lesions
- 2. Objective quantification of the impairment caused by new ischemic brain injury assessed using the National Institutes of Health Stroke Scale (NIHSS)
- 3. Delirium assessed using the 3-minute diagnostic interview for Confusion Assessment Method (CAM)
- 4. Functional status assessed using the Barthel Index score
- 5. Neurocognitive function in 6 domains (verbal memory, visual memory, executive functioning, visuospatial or constructional praxis, attention, and information processing speed), assessed using the following tests:
 - a. Addenbrooke's Cognitive Examination III (ACE III)
 - b. Oral Trail making Tests A and B (oTMT A&B)
- 6. Quality of life assessed using the physical and mental subscales of the 12-Item Short-Form Health Survey (SF-12)
- 7. Composite of all-cause mortality, clinical stroke, or acute kidney injury within 30 days of surgery
- 8. Serious adverse events (SAEs) to 3 months
- 9. Survival to 3 months

All patients will be consented for passive follow up for up to five years after their surgery from NHS and national health and registration records to determine any association between silent brain lesions and long-term neurological outcomes (e.g. dementia).

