9.4 Period for recording serious adverse events

Data will be collected on all SAEs that occur from randomisation until the three-month follow up visit using the relevant CRFs.

Centres should expedite reporting of all fatal and 'unexpected' non-fatal SAEs that occur between randomisation and discharge to BTC CTEU within 24 hours of becoming aware, using an SAE report form.

The BTC CTEU will report all fatal and 'unexpected' non-fatal SAEs to the Sponsor. Unexpected events are those not listed in the trial protocol or on the CRFs. The Sponsor will report SUSARs to the MHRA and copy all reports to the BTC CTEU. BTC CTEU will report SUSARS to the REC.

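### The AKI component of secondary outcome 7 runs to 30 days, but sections 6.8 and 9.3 and Table 1 stop recording non-serious AKI at discharge, and section 8(g) contradicts them

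*Protocol*

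**What the plan says.** Section 5.1.2 defines secondary outcome 7 as "Composite of all-cause mortality, clinical stroke, or acute kidney injury within 30 days of surgery".

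The recording rules are set in several places:

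- Section 9.3: "Data on adverse events will only be collected for the period of the" post-operative hospital stay.
- Section 9.4: "Data will be collected on all SAEs that occur from randomisation until the three-month follow up visit using the relevant CRFs".
- Section 6.8 lists both AEs and SAEs for the inpatient stay, but for the period afterwards only "Collection and assessment of any SAEs experienced after discharge from hospital".
- In Table 1 the only event row that continues past discharge is "Assessment of serious adverse events (from randomisation to three month follow up), including readmissions". The row for post-operative complications has a single tick, in what reads as the discharge column.
- Section 8, item (g), says that adverse events are among the data gathered from every participant at three months.
- Section 10.1 places case report forms at discharge, the routine post-operative appointment and three months, with hospital notes as the main source.

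Table 2 (section 9.6) lists AKI among the anticipated adverse events of surgery.

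**The concern.** The outcome has a fixed window of 30 days for everyone. For AKI that is not serious, section 9.3 replaces it with a window that ends when the patient goes home and so differs from patient to patient. What would be reported as 30-day AKI would in practice be AKI during the index stay plus serious AKI to day 30.

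The conflict with section 8(g) adds a second difficulty. A centre that follows 9.3 and Table 1 would not record a non-serious AKI after discharge; a centre that follows section 8 would. The same event could then count at one centre and not at another.

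The analysis plan cannot repair this. It can define AKI and say how the composite is built, but it cannot recover events that sites were told not to record. At stake are the meaning and the event rate of one component of one of nine secondary outcomes.

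**Working it through.** **Step 1. The plan's own figures.** The protocol states no rate, power or sample size for outcome 7 or for AKI. Its main sample size concerns the primary outcome only. For completeness, with 48% v 36%, two-sided 5% and 90% power, n per group = [1.960 × √(2 × 0.42 × 0.58) + 1.282 × √(0.48 × 0.52 + 0.36 × 0.64)]² / 0.12² ≈ 354, or 708 in total, against the stated 704. Power at 352 per group is 89.9%. That figure reproduces and has no bearing on this point.

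**Step 2. Which parts of the composite are recorded to day 30.**

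| Event | Recording route | Covered to day 30? |
|---|---|---|
| Death | SAE, section 9.4 | Yes |
| Stroke meeting a seriousness criterion | SAE, section 9.4 | Yes |
| AKI during the index stay | Section 9.3; complications row of Table 1 | Yes, for in-hospital onset |
| AKI after discharge, serious (including readmission) | SAE, section 9.4; Table 1 | Yes |
| AKI after discharge, not serious | None under 6.8, 9.3 and Table 1; open under 8(g) | Depends on which section is followed |

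Only the last row is a gap. The seriousness criteria in section 9.2 are broad (admission, prolonged stay, disability, or an event needing intervention to prevent such outcomes), so that row is narrow.

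**Step 3. What the gap could do to the comparison.** The inputs needed are not in the protocol, so the values here are assumptions that show direction and scale only. Let L be the share of 30-day non-serious AKI that begins after discharge in the placebo group, and d the extra share missed in the CDI group because of a shorter stay. With equal true risk in both groups:

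ratio of recorded risks = (1 − L − d) / (1 − L)

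| L | Placebo capture, 1 − L | d = 0 | d = 2 points | d = 5 points |
|---|---|---|---|---|
| 5% | 95% | 1.00 | 0.93/0.95 = 0.98 | 0.90/0.95 = 0.95 |
| 10% | 90% | 1.00 | 0.88/0.90 = 0.98 | 0.85/0.90 = 0.94 |
| 20% | 80% | 1.00 | 0.78/0.80 = 0.98 | 0.75/0.80 = 0.94 |

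With equal stays (d = 0) the recorded rate falls but the ratio stays at 1.00. A ratio other than 1.00 needs a difference in stay. The ratios apply to non-serious AKI alone; the composite also holds death, stroke and serious AKI, which are captured, so any shift in the composite would be smaller.

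**Step 4. Centres following different sections.** Randomisation is stratified by centre (6.5) and the analysis adjusts for centre (11.3). Differences between centres in recording therefore fall on both groups alike. They affect the event rate and its interpretation more than the comparison.

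**The case against.** The strongest reply is that section 9.3 belongs to the safety-reporting chapter, whereas outcome 7 is a trial outcome whose data come under sections 8 and 10.1. On that reading, 8(g) and the forms at routine follow-up and three months already supply the data, and dated events can be taken from hospital notes. It is also fair to say that a 30-day window needs no visit on day 30.

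The last point stands: the absence of a 30-day contact is not a defect. The rest stands only in part. Section 10.1 does not name AKI. Sections 6.8 and 9.3 and Table 1 agree with each other against 8(g). If 8(g) uses adverse events loosely to mean SAEs, the contradiction disappears but the gap is certain. If it is meant literally, the gap closes but the other three places are wrong. Either way the text needs correcting.

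Two stronger readings are tempting. A reader might infer that the composite as a whole cannot be measured as defined. Section 9.4 does not support that, since most of what the composite counts is collected to three months.

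A reader might also infer a bias in favour of CDI, because section 3 describes ischaemic brain injury as "associated with increased hospital stay, slow recovery", so that a working treatment would shorten the stay and with it the time under observation. That is a possible route, and blinding would not close it if the effect on recovery were real. But section 3 reports an association and says nothing about CDI and length of stay. Section 2.2 says that few lesions (about 9%) come with overt clinical signs, which makes a material effect on average stay doubtful. Blinding of the care teams (6.6) removes knowledge of allocation as a cause of earlier discharge. The documents do not show this bias.

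**Conclusion.** The point holds in a limited form. The 30-day window of the AKI component and the recording rules do not match, and the protocol contradicts itself on whether adverse events are collected after discharge. The loss is confined to non-serious AKI that begins between discharge and day 30.

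The effect is probably small, and its size cannot be derived from the protocol. The ratios of 0.94 to 0.98 above depend wholly on assumed differences in stay and are not estimates. The conclusion assumes that a clinical stroke within 30 days would meet a seriousness criterion, and that the complications row of Table 1 is ticked at discharge, as the extracted table suggests. This is a minor correction to one secondary outcome; the primary outcome and the sample size of 704 are untouched.

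**What to change.** First reconcile section 8(g) with sections 6.8 and 9.3 and Table 1, so that every centre works from one rule on adverse events after discharge. Then do one of the following:

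- **(a) Match the outcome to the data.** Restate the component as AKI during the index stay, or within a fixed early post-operative period, plus AKI meeting SAE criteria to day 30, and label it so. A fixed early period has the advantage of a common window if it falls inside the stay of nearly all patients. The cost is a change of wording and a slightly narrower outcome.
- **(b) Match the data to the outcome.** Make AKI to day 30 an exception in 9.3, collected with onset dates from hospital notes at the routine and three-month follow-ups already scheduled. The cost is one more data item. The yield may be low, since an episode that needed no admission will be found only if it was documented.

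Option (a) is the cheaper and describes what can reliably be observed; option (b) keeps the 30-day label.
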